#### 445      Safety Outcomes: Severe Hypoglycemia and DKA events, and hospitalizations

### 447      **6.4 Description of Statistical Methods**

#### 448      **6.4.1 Analysis Cohorts**

449      All subjects enrolled in the study who initiate the CGM and have a minimum amount of data as  
450      defined in the SAP will be included in the tabulations of baseline and the efficacy analyses. All  
451      subjects enrolled in this study will be included in the safety analyses.

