### 452      **6.5 Analysis of Efficacy Outcomes**

453      CGM metrics and HbA1c will be calculated and summarized at 13, 26, 39, and 52 weeks.  
454      Summary statistics for questionnaires will be provided at all time points when they are collected.

455 A linear mixed model with a random subject effect will be used to assess whether the change  
456 from baseline significantly differs from zero. If values are highly skewed, then the winsorized  
457 mean will be tested or a transformation utilized. A complete-case analysis using a paired t-test or  
458 Wilcoxon signed rank test will also be assessed.

459 **6.6 Subgroup Analyses**

460 Subgroup analyses for HbA1c and selected CGM outcomes will be performed by baseline  
461 HbA1c group, insulin delivery modality, age, healthcare provider (endocrinologist or primary  
462 care provider), and various participant characteristics as described in the SAP.

463 **6.7 Safety Analyses**

464 All adverse events that occur post enrollment will be listed in a table. Additionally, each of the  
465 following safety metrics will be tabulated for reported SH and DKA events, hospitalizations and  
466 emergency room visits:

467     • Number of subjects with  $\geq 1$  event  
468     • Number of events per subject  
469     • Incidence rate per 100 person-years

470 **6.8 Baseline Descriptive Statistics**

471 Baseline demographic and clinical characteristics of the cohort of all subjects who initiate the  
472 CGM will be summarized in a table.

473 **6.9 Multiple Comparisons/Multiplicity**

474 No adjustments for multiple comparisons will be made.

475 **6.10 Additional Analyses**

476 Several additional analyses will be performed in this study. These will include the following:

477     • Tabulations of CGM glycemia and CGM use by month and comparing the first 26 weeks  
478 and last 26 weeks of the study (overall and within subgroups)  
479     • Tabulations of CGM glycemia by time of day  
480     • Tabulations of the number of participant contacts with the virtual clinic  
481     • Bivariate relationship between questionnaires and glycemic metrics following CGM  
482 initiation

483 **Chapter 7: Ethics/Protection of Human Participants**

484 **7.1 Ethical Standard**

485 The investigator will ensure that this study is conducted in full conformity with Regulations for  
486 the Protection of Human Participants of Research codified in 45 CFR Part 46, 21 CFR Part 50,  
487 21 CFR Part 56, and/or the ICH E6.

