The goal for the study is to include at least 300 participants who initiate CGM. This is a convenience sample and not based on statistical principles.

5 Outcome Measures

The following quantitative study outcome measures will be tabulated by diabetes type using summary statistics appropriate to the distribution:

- HbA1c
- Percentage of time using the CGM
- Hours of CGM use
- Mean of sensor glucose levels
- Percentage of time spent with sensor glucose levels <54 and <70 mg/dL
- Percentage of time spent with sensor glucose levels >180 and >250 mg/dL
- Percentage of time spent with sensor glucose levels in the target range (70-180 mg/dL)
- Glycemic variability measured by the coefficient of variation
- Total daily insulin (units/kg)
- Total daily basal insulin (units/kg)
- Total daily bolus insulin (units/kg)
- Patient Health Questionnaire-8
- Diabetes Distress Scale Management Distress Subscale
- Hypoglycemia Fear Survey Worry Subscale
- CDC Healthy Days
- Hypoglycemia Confidence Survey
- Diabetes Technology Attitudes Survey
- Glucose Monitoring Satisfaction Survey
 - Openness Subscale
 - Emotional Burden Subscale
 - Behavioral Burden Subscale
 - Trust Subscale
- Sleep Quality Scale
- Benefits and Barriers of CGM Survey
- Percentage of CGM discontinuations
- CGM Discontinuation Survey (only administered to subjects who discontinue CGM)
- Positive screen for mental health

41 ○ Positive screen triggered by Patient Health Questionnaire-8
 42 ○ Positive screen triggered by Diabetes Distress Scale
 43 ○ Positive screen triggered by Hypoglycemic Fear Survey Worry Scale
 44 • Behavioral health service utilization
 45 • Behavioral health metrics
 46 • Cost of care over time
 47 • Service utilization such as hospitalizations, ER visits, prescriptions filled

48
 49 CGM, HbA1c, and insulin outcomes will be evaluated at baseline and 13, 26, 39, and 52 weeks.
 50 CGM and insulin outcomes will also be evaluated over the first 26 weeks and last 26 weeks.
 51 Questionnaires will be evaluated at all time points they are collected.

52 **6 Description of Statistical Methods**

53 **6.1 Analysis Cohorts**

- 54 • All subjects enrolled in the study who initiate the CGM and have at least 168 hours of
 55 CGM data will be included in the tabulations of demographics and the glycemic
 56 outcome measures listed in Section 5
- 57 • CGM use assessment will include all subjects who stayed in the study at least one week
 58 following CGM initiation.

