- 59 • HbA1c, questionnaires, insulin, and other analyses will include all subjects with any
 60 amount of corresponding data following CGM initiation.
- 61 • The tabulations of the safety outcomes will include all participants who enrolled,
 62 regardless of how much data is available.

63 **7 Analysis of Study Endpoints**

64 **7.1 Calculation of CGM Metrics**

65 **7.1.1 Calculation of 13 Week CGM Metrics**

66 All CGM metrics listed in Section 5 will be calculated on a 13-week period for each subject
 67 level. The windows for the 13-week periods are defined as follows:

Time Point	Window
1-13 Weeks	0 to 91 days after the CGM initiation date
14-26 Weeks	92 to 183 days after the CGM initiation date
27-39 Weeks	184 to 274 days after the CGM initiation date
40-52 Weeks	275 to 365 days after the CGM initiation date

68
 69 For each 13-week period, CGM metrics will be calculated by pooling all CGM readings
 70 occurring from 12:00 AM on the first day of the 13-week period up until 11:59PM on the last
 71 day of the 13-week period. For the first 13-week period, the first CGM reading will be the start
 72 datetime of the period. If a participant discontinues CGM prior to the last day of the 13-week
 73 period, then CGM data will include readings up to the last CGM reading on the discontinuation
 74 date. Calibrations will be excluded from all these calculations. CGM metrics for 13-week periods
 75 with less than 168 hours of CGM data will be set to missing.

76 Baseline CGM metrics will be calculated by pooling all blinded CGM readings up to 90 days
77 prior to the date of CGM initiation for each subject. Baseline CGM metrics with less than 72
78 hours of CGM data will be set to missing.

79 The amount of time using the CGM will be calculated as the number of CGM values multiplied
80 by the expected CGM measurement frequency (i.e., 5min in general), with the exception that
81 there can only be one value within the CGM measurement frequency. Percentage of time CGM
82 is used will be calculated as the amount of time using the CGM divided by the total possible time
83 the participant could have used the CGM during the same period. Note that this denominator
84 includes sensor warm-up periods with no CGM values, so this metric will serve as a conservative
85 estimate of CGM use.

86 **7.1.2 Calculation of 4 Week CGM Metrics**

87 All CGM metrics listed in Section 5 also will be calculated on a 4-week interval for each subject.

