7.4 Statistical Methods

For all outcomes, summary statistics appropriate to the distribution will be tabulated on a subject level overall and within the subgroups defined in Section 12. For the CGM metrics, summary statistics appropriate to the distribution also will be tabulated for each 4-week interval and for the first and last 26 weeks of the study. For the questionnaires, summary statistics will be reported for the mean scores in addition to the individual responses for each question.

For all outcomes, a linear mixed model with a random subject effect will be used to test whether the mean change from baseline significantly differs from zero. These models will be fit for each of the subject level CGM metrics and HbA1c at 13, 26, 39, and 52 weeks. They also will be fit for the questionnaires at 26 and 52 weeks. If values are skewed, then winsorization will be utilized. Point estimates and 95% confidence intervals for change in glycemic outcomes will be reported.

For the three mental health screening questionnaires, only summary statistics will be tabulated. The three mental health screening questionnaires falling under this umbrella are the Patient

187 Health Questionnaire-8, the Diabetes Distress Scale (Management Distress Subscale), and the
188 Fear of Hypoglycemia Survey (Worry Subscale).

189 **7.5 Analyses Windows**

190 For HbA1c, only measurements occurring within ± 45 days of the target measurement date at a
191 given time point will be included in the tabulation of summary statistics. The windows for
192 glycemic metrics were defined above in Section 7.1.

193 **7.6 Sensitivity Analyses**

194 For CGM and HbA1c outcomes, a complete-case analysis restricting to non-missing outcomes
195 will also be assessed. A paired t-test (for normally distributed outcomes) or a Wilcoxon signed
196 rank test (for skewed outcomes) will be used.

197 **8 Safety Analyses**

198 All adverse events that occur on or after the date of enrollment will be listed in a table.

199 For events occurring on or after the date of CGM initiation, the reported safety outcomes include
200 diabetic ketoacidosis (DKA), severe hypoglycemia (SH), hospitalization, and emergency room
201 visits. The following statistics will be tabulated for each safety outcome:

- 202 • Total number of events
- 203 • Number and proportion of subjects with an event (discretized into bins)
- 204 • Incidence rate per 100 person years

205

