206 The number of person-years for the incidence rate calculations will be inclusively defined as the
207 number of person-years in between the CGM initiation date and the last day of study follow-up
208 (completion date, withdrawal date, etc.).

209 **9 Adherence and Retention Analyses**

210 **9.1 Protocol Adherence**

211 The number of and reasons for participant contacts with the virtual clinic will be reported in a
212 table to assess protocol adherence for the study.

213 **10 Baseline Descriptive Statistics**

214 Baseline demographic and clinical characteristics of the cohort of all subjects who initiate the
215 CGM and were included in the glycemic analyses will be summarized in a table. Use of
216 medications and non-insulin therapy will also be reported. For continuous variables, summary
217 statistics appropriate to the distribution will be given. For discrete variables, number and
218 percentage will be reported for each category. Summary statistics for demographics and clinical
219 characteristics will be presented overall, by diabetes type, by insulin modality, by whether the
220 participant was seeing an endocrinologist or a primary care provider at baseline, by baseline
221 HbA1c groups ($<7.5\%$, 7.5% to $<9.0\%$, and $\geq 9.0\%$), and by age (<25 , $25\text{-}65$, and >65 years). Cut
222 points for age and baseline HbA1c may be reassessed after data are collected.

223 **11 Planned Interim Analyses**

224 No formal interim analyses or stopping guidelines are planned for this study. Data will be
225 monitored on an ongoing basis including:

- 226 • Status of enrolled participants
- 227 • Recruitment rates by month and by site
- 228 • Baseline demographic and clinical characteristics
- 229 • Dropped participants and reasons for discontinuing
- 230 • Reportable adverse events

231 **12 Subgroup Analyses**

232 Subgroup analyses for % of time using the CGM, % time in range, % time >180 mg/dL, % time
233 <70 mg/dL, and HbA1c will be performed based on the following factors:

- 234 • Baseline HbA1c (categorized as <7.5%, 7.5% to <9.0%, and ≥9.0%)
- 235 • Insulin modality
- 236 • Age (categorized as <25, 25-65, and >65)
- 237 • Type of healthcare provider (endocrinologist or primary care provider)
- 238 • Diabetes Duration (categorized as <5, 5-<10, 10-<20, ≥20)
- 239 • Race/Ethnicity
- 240 • Household income (categorized as <\$50,000, \$50,000-<\$100,000, and ≥\$100,000)

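### Minor: SAP 8 tabulates safety events only from CGM initiation while SAP 6.1 sets the cohort as all enrolled, so any enrolled participant who never starts CGM dilutes the proportion with an event

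*SAP*

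**What the plan says.** **Cohort.** SAP 6.1 says "The tabulations of the safety outcomes will include all participants who enrolled" and waives any minimum amount of data. Protocol 6.4.1 agrees: all "subjects enrolled in this study will be included in the safety analyses".

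**Event window.** SAP 8 narrows the four tabulated outcomes: "For events occurring on or after the date of CGM initiation, the reported safety outcomes include" DKA, severe hypoglycemia, hospitalization and emergency room visits. Among the statistics requested is "Number and proportion of subjects with an event (discretized into bins"). No denominator is given there.

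**Exposure.** The incidence rate in SAP 8 uses the "number of person-years in between the CGM initiation date and the last day of study follow-up".

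**Listing.** SAP 8 separately lists every adverse event from the enrollment date. Protocol 6.7 has the same listing: "All adverse events that occur post enrollment will be listed in a table".

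**Protocol tabulation.** Protocol 6.7 says the "following safety metrics will be tabulated for reported SH and DKA events, hospitalizations and" emergency room visits, and sets no start date at CGM initiation. It asks for the number of subjects with at least one event, events per subject and an incidence rate. The proportion is requested only in SAP 8.

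**Enrolled versus initiated.** SAP 6.1 treats the initiators as part of a wider enrolled set, since its glycemic cohort is "All subjects enrolled in the study who initiate the CGM and have at least 168 hours of" CGM data.

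**The concern.** A proportion is interpretable when everyone in the denominator could have contributed to the numerator. Read together, SAP 6.1 and SAP 8 break that rule for any enrolled participant who leaves before starting CGM. Such a person is counted in the denominator, while the event window never opens.

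The documents provide routes out in that interval. Protocol 2.7 drops participants whose blinded data cannot be obtained, or who have a serious skin reaction in blinded wear that rules out further sensor use. Protocol 5.5 allows withdrawal of those who do not complete baseline procedures in time.

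Two consequences would follow. The proportion with an event would fall as loss before initiation rises, which says nothing about safety on CGM. And the proportion and the incidence rate, printed in the same table, would describe different groups.

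**Working it through.** The plan gives no expected safety proportion or event rate, so there is no figure of its own to reproduce. The check is arithmetic on the stated definitions.

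**Inputs**
- Initiators, I = 300: the recruitment target in SAP 4 and Protocol 6.2.
- Enrolled, N: not given. Assumed values 300, 315, 330 and 400.
- Participants with at least one severe hypoglycemia event after initiation, x = 15: assumed, for illustration only.

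**Formulas**
- Proportion among initiators = x / I.
- Proportion under the SAP 6.1 cohort = x / N.
- Ratio of the second to the first = I / N, whatever x is. Relative understatement = 1 − I / N.
- Zero-event bin under the SAP 6.1 cohort = N − x.

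**Results**

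| N (assumed) | Never start CGM | 1 − 300/N | 15/N | Zero-event count | Zero-event share |
|---|---|---|---|---|---|
| 300 | 0 | 0% | 5.00% | 285 | 95.00% |
| 315 | 15 | 15/315 = 4.8% | 4.76% | 300 | 95.24% |
| 330 | 30 | 30/330 = 9.1% | 4.55% | 315 | 95.45% |
| 400 | 100 | 100/400 = 25.0% | 3.75% | 385 | 96.25% |

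**Incidence rate.** A participant who never starts CGM adds 0 events and 0 person-years. With one event in each of 15 participants and, for illustration, one year of follow-up for each of 300 initiators, the rate is 100 × 15 / 300 = 5.0 per 100 person-years at every N.

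**Unaffected quantities.** The number with an event stays at 15, and total events do not depend on N. The adverse event listing runs from enrollment, so earlier events remain visible there.

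**The case against.** **The cohort sentence may have a narrower purpose.** It follows three bullets that each set a data or time-in-study requirement, and it ends by waiving any such requirement. One can read it as doing only that, and read SAP 8, the more specific section, as implying an initiator denominator. That is a reasonable reading, but SAP 8 does not state it. The only population that the SAP names for these tabulations is all enrolled.

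**The table shells may settle it.** They are a separate document, and the denominator of each table could be shown there. This limits certainty about what will be printed. It does not remove the mismatch in the SAP text.

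**The gap may be empty.** Consent is signed to begin screening (Protocol 2.1), blinded CGM is described under screening (Protocol 2.4), and a skin reaction in blinded wear is an exclusion criterion (Protocol 2.3). Some or all of those who leave early may therefore be screen failures and not enrolled. This stands, and it is why the size cannot be fixed.

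**The effect is modest.** With 15 of 300, the Wilson 95% interval is about 3.1% to 8.1%, which contains all the diluted values in the table. The study is single-arm and exploratory, no test or stopping rule uses the proportion, and a reader told the number of initiators could recompute it. This also stands, and it keeps the point minor.

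**The difference from the Protocol may be one of versions.** The SAP is based on Protocol Version 2.0, and its eligibility text on CGM users differs from the Protocol text reviewed here. The missing post-initiation limit in Protocol 6.7 may have the same origin. The mismatch between SAP 6.1 and SAP 8 lies within one document, so versions do not explain it.

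**Conclusion.** The mismatch within the SAP is confirmed. Under its stated rules, each enrolled participant who never initiates CGM lowers the proportion with an event and enlarges the zero-event bin. If there are such participants, the direction is certain: the proportion is multiplied by initiators/enrolled. At 300 initiators the understatement would be 4.8% with 315 enrolled and 9.1% with 330. Both enrolled totals are assumptions.

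A reader might infer three stronger things that the documents do not support:
- **That the proportion will certainly be diluted.** This needs at least one person who counts as enrolled and does not start CGM. Since *enrolled* is undefined, that number may be zero.
- **That the understatement could be expected to reach 1 − 300/800 = 62.5%.** The 800 in Protocol 2.1 is a ceiling on consents signed to begin screening and would include screen failures. It is not a forecast of enrollment.
- **That safety events are lost or rates biased.** Counts and incidence rates do not change with the denominator, and events from enrollment onward are listed.

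This is a minor point that deserves a wording correction.

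**What to change.** In SAP 6.1 and SAP 8:
- Use all participants who initiated CGM, with no minimum-data rule, as the denominator for post-initiation proportions and bins. This matches the person-years.
- Keep all enrolled participants for the adverse event listing, and show events between enrollment and CGM initiation separately.
- Define *enrolled* and give both the number enrolled and the number who initiated.
- Note that the initiator denominator narrows the cohort in Protocol 6.4.1, and that Protocol 6.7 has no post-initiation limit.

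Counting events and person-years from enrollment over all enrolled would also be consistent, and closer to the Protocol. It is less attractive because adverse events are part of follow-up data collection (Protocol 3.6) and the follow-up questionnaires are scheduled after CGM initiation. Earlier events would rest mainly on reports to staff (Protocol 5.1) or questionnaires at withdrawal (Protocol 5.5).

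The cost is wording, with no new data. Aligning the Protocol text as well would need IRB review (Protocol 7.2). Compared with the all-enrolled denominator, reported proportions are multiplied by enrolled/initiators: 1.00 (no change) if everyone enrolled initiates, 315/300 = 1.05, or 330/300 = 1.10. They would look slightly less favourable.
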